5.4.2.3 HBeAg Seroclearance and Seroconversion 5.4.2.4 HBsAg, HBeAg, HBV DNA and ALT 5.4.2.4.3 HBeAg Thresholds	Updated text for HBeAg analyses which will be performed only for HBeAg positive participants at study entry.	Improved language for clarity and precision.
5.4.2.4.9 Thresholds On Multiple Markers	Added two thresholds HBsAg and HBV DNA thresholds	Additional analyses for HBsAg and HBV DNA thresholds were decided to be performed after approval of the original SAP (dated 14 June 2022).
5.4.2.7.2. Time to Flare 5.4.2.8.2. Time to HBV Virologic Breakthrough	These sections were removed due to reduced sample size.	Time to event analyses were removed due to reduced number of events for this type of analysis.
Partial Cure	Removed the partial cure endpoint and analysis.	The initial planned analysis of this endpoint is covered by other analyses.
5.5.6 Sustained HBsAg Response	Added section with definitions of HBsAg sustained response and their analyses.	Additional analysis for HBsAg was included to better characterize off-treatment HBsAg response.

Clarifications, Additions, Corrections		
Section Number and Name	Description of Change	Rationale
5.7.3 Viral Genome Sequence Analysis	Removed subsections.	Subsections were removed to simplify the analysis.
5.7.4 Definition of Subgroups	Removed some subgroups.	Considering the small sample size, it was decided to remove some subgroups.
Medications of Special Interest	Removed the medications of special interest section.	Removal due to discontinuation of JNJ-6379.
7 References	Removed references related to Viral Genome Sequencing.	References were removed due to removal of the subsections from the Viral Genome Sequencing section.
Throughout the document	Clarification of text.	Typographical corrections or improved language for clarity and precision.

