1.2. Study Design

A target of 24 chronic HBV-infected male and female participants, 18-65 years (inclusive) of age

will be enrolled in Panels 1 and 2, approximately 12 participants in each panel. In Panel 3, a target of 4-6 chronic HBV-infected male and female participants will be enrolled.

- Panel 1 will consist of participants who are HBeAg positive and not currently treated.
- Panel 2 will consist of participants who are HBeAg negative and virologically suppressed by ETV, TD, or TAF treatment.
- Panel 3 will consist of participants who are HBeAg positive or negative and are either not currently treated or virologically suppressed by ETV or TD treatment.

The study will be conducted in 3 phases for all participants:

- A **screening phase** (4 to 6 weeks),
- An **open-label study intervention phase** (48 weeks),
- A **follow-up phase** (48 weeks). Note that the follow-up period will be extended up to an additional 24 weeks for participants who are receiving optional treatment with PegIFN- α 2a and who meet NA treatment completion criteria at the end of treatment with NA and PegIFN- α 2a to ensure all participants have at least one year of follow-up after NA treatment cessation.

The duration of individual participation will be up to 102 weeks for participants who stop NA treatment at the end of the open-label phase, or up to 126 weeks for participants who stop NA treatment during the follow-up phase.

Prior to Protocol Amendment 5, in Panels 1 and 2, participants were randomized in a 1:1 ratio within each panel to receive one of the following interventions (i.e., treatments) for 48 weeks:

- **Arm 1**, combination regimen JNJ-3989+JNJ-6379+NA:
 - 200 mg JNJ-3989 (SC injection Q4W, with the last injection at Week 44), and
 - 250 mg JNJ-6379 (tablets qd), and
 - NA: ETV, TD, or TAF (tablets qd)
- **Arm 2**, combination regimen JNJ-3989+NA:
 - 200 mg JNJ-3989 (SC injection Q4W, with the last injection at Week 44), and
 - NA: ETV, TD, or TAF (tablets qd).

As of Protocol Amendment 5, in Panels 1 and 2, participants who were previously randomized to Arm 1 had to stop JNJ-6379 treatment immediately but will still receive JNJ-3989 and NA – effectively joining Arm 2. New participants will enroll without randomization to Arm 2.

No participants were enrolled in Panel 3 before Protocol Amendment 5 was in effect. Therefore, all Panel 3 participants will enroll without randomization to receive the Arm 2 regimen.

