In addition, participants who provide separate consent may receive optional treatment with PegIFN- α 2a starting after the Week 40 biopsy (or after the optional leukapheresis if applicable) but before the Week 48 visit. The duration (either 12 or 24 weeks) will be at the investigator's

discretion. This will allow investigation of whether addition of PegIFN- α 2a for 12 or 24 weeks may increase the participant's chance to achieve HBsAg loss.

All participants will complete treatment with JNJ-3989 after a fixed duration of 48 weeks. Treatment with NA will also be completed at Week 48 except for participants not meeting the NA treatment completion criteria (outlined in Protocol Section 6.6.1). In participants not meeting these criteria, NA treatment will continue during the follow-up phase. Participants who are receiving optional treatment with PegIFN- α 2a and who have not met NA treatment completion criteria at Week 48 may have NA treatment completion criteria assessed at the end of treatment with PegIFN- α 2a and stop NA if criteria are met.

[figure not shown]
In case of premature discontinuation of study agent JNJ-3989 (before Week 48), follow-up assessments should be obtained until 48 weeks after End Of Study Intervention (EOSI) unless the participant withdraws consent. Participants who withdraw consent will be offered an optional safety follow-up visit.

The SAP will use throughout the document the following definitions:

- *Study treatment* refers to JNJ-6379, JNJ-3989, NA (either ETV, TD, or TAF), and PegIFN- α 2a.
- *Study agent* refers to JNJ-6379 and JNJ-3989
 - *Arm* refers to:
 - Arm 1: JNJ-3989+JNJ-6379+NA
 - Arm 2: JNJ-3989+NA

A schematic overview of the study is presented in [Figure 1](#) (Prior to Protocol Amendment 5) and in [Figure 2](#) (As of Protocol Amendment 5).

[figure not shown]
Figure 1: Schematic Overview of the Study – Prior to Protocol Amendment 5

ETV: entecavir; N: number of participants; LB: (planned) liver biopsy; NA: nucleos(t)ide analog; Q4W: once every 4 weeks; qd: once daily; TAF: tenofovir alafenamide; TD: tenofovir disoproxil; QW: once weekly

* Participants who provide separate consent may receive optional treatment with PegIFN- α 2a starting after the Week 40 biopsy (or after the optional leukapheresis visit if applicable) for a duration of either 12 or 24 weeks at the investigator's discretion.

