5. STATISTICAL ANALYSES

5.1. General Considerations

5.1.1. Analysis Phase

The analysis phases are defined in [Table 1](#) below. Note that the screening, open-label, and follow-up phases are non-overlapping and cover the entire study period. The optional PegIFN- α 2a treatment phase, in contrast, may overlap with both the open-label and follow-up phases.

Table 1: Analysis Phases Start and End Dates

Analysis phase	Start date	End date
Screening	The date of signing the informed consent	1 day before the first study agent intake (JNJ-3989 or JNJ-6379)
Open-label study intervention	Date of first study agent intake (JNJ-3989 or JNJ-6379)	Earliest of the following dates: 
 • Early discontinuation date for JNJ-3989 + 5 days^a • Study termination date • Max{ 
 • Date of last JNJ-3989 intake, • Date of Week 48 visit • } + 5 days^a • Cut-off date^b
Follow-up	End date of open-label phase + 1 day	Min (study termination date, study completion date, cut-off date ^b)
Optional PegIFN- α 2a treatment	Date of first PegIFN- α 2a intake	Min (Date of last PegIFN- α 2a intake + 5 days ^a , cut-off date ^b)

a : Addition of 5 days is only applicable for Adverse Events and Concomitant Medications.

b : Cut-off dates will be defined to match the prespecified timepoints for interim analyses, the primary analysis and the final analysis, respectively.

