	last visit in open-label phase	49 ^a	EOT ^a	

^a End of treatment (EOT) visit will be the last post-baseline visit in open-label phase as defined in [Table 1](#).

b) Follow-Up Phase

Analysis phase	Target day	Analysis time point (Week)	Analysis time point (Label)	Follow-up time interval (Days)
Follow-up	15	50	Follow-up Week 2	[1, 22]
	29	52	Follow-up Week 4	[23, 43]
	57	56	Follow-up Week 8	[44, 71]
	85	60	Follow-up Week 12	[72, 99]
	113	64	Follow-up Week 16	[100, 127]
	141	68	Follow-up Week 20	[128, 155]
	169	72	Follow-up Week 24	[156, 183]
	197	76	Follow-up Week 28	[184, 211]
	225	80	Follow-up Week 32	[212, 239]
	253	84	Follow-up Week 36	[240, 267]
	281	88	Follow-up Week 40	[268, 295]
	309	92	Follow-up Week 44	[296, 323]
	337	96	Follow-up Week 48	[324, $+\infty$)
	365	100	Follow-up Week 52 (Ext)	[352, 379]
	393	104	Follow-up Week 56 (Ext)	[380, 407]
	421	108	Follow-up Week 60 (Ext)	[408, 435]
	449	112	Follow-up Week 64 (Ext)	[436, 463]
	477	116	Follow-up Week 68 (Ext)	[464, 491]
	505	120	Follow-up Week 72 (Ext)	[492, $+\infty$)
	last visit in the study	999 ^a	EOS ^a	

^a End of study (EOS) visit (last available data during the follow-up phase) will be the last visit in the study.

Note: The visits labeled with “Ext” are only for participants who completed PegIFN administration and NA treatment during the follow-up phase.

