5.5.6. Sustained HBsAg Response

The definitions of sustained response are as follows:

Definition 1 (yes/no):

- For participants with data at the last scheduled follow-up visit (Follow-up Week 48 for participants who did not receive PegIFN- α 2a or received PegIFN- α 2a and did not meet NA completion criteria, and last Follow-up visit for participants who received PegIFN- α 2a and stopped NA during Follow-up): Participants who have a > 1 log decline in HBsAg at last scheduled follow-up visit and have an HBsAg < 1000 IU/mL at the last scheduled follow-up visit.
- For participants without data at the last scheduled follow-up visit: HBsAg values have a > 2 log decline at the second most recent visit or > 1.5 log decline at the latest visit (most recent value used) compared to baseline and have an HBsAg < 1000 IU/mL at the last available timepoint.

Definition 2 (yes/no): For participants with a > 1 log decline in HBsAg from baseline at last follow-up visit: Among the most recent three visits, the difference between log HBsAg at 2 of 3 last visit and 1 of 3 last visit is < 0.2 , and the difference between log HBsAg at 3 of 3 last visit and 1 of 3 last visit is < 0.2 .

Definition 3 (yes/no): For participants with a > 1 log decline in HBsAg from baseline at last follow-up visit: Among the most recent three visits, the difference between log HBsAg at 2 of 3 last visit and 1 of 3 last visit is < 0.2 , and the difference between log HBsAg at 3 of 3 last visit and 1 of 3 last visit is < 0.2 and have an HBsAg < 1000 IU/mL at the last available timepoint.

Definition 4 (>0.2 log increase, $+/-0.2$ log, >0.2 log decline): Three categories regarding the difference between HBsAg level at the last Follow-up timepoint and EOT:

- $>0.2 \log_{10}$ decrease: Decreasing level
- $\leq 0.2 \log_{10}$ increase or $\leq 0.2 \log_{10}$ decrease: Stable level
- $>0.2 \log_{10}$ increase: Increasing level

Due to the exploratory objectives of this Phase 2 study, additional sustained HBsAg response definitions may be explored according to the clinical interest.

For all definitions of the sustained HBsAg response, only participants with at least 24 weeks after JNJ-3989 stop will be used for the analysis.

The count and proportion (%) of participants achieving sustained HBsAg response will be summarized.

Spaghetti plots for HBsAg actual values and change from baseline will be presented by study panel over time using color coding by category.

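### SAP 5.5.6 Definition 4 measures the HBsAg trend from about Week 48, when most PegIFN-α2a recipients are still on PegIFN, so a fall on PegIFN is netted against any rebound after it

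*SAP*

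**What the plan says.** SAP 5.5.6 gives four definitions of sustained HBsAg response.

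- Definition 1 uses the log decline and a level below 1000 IU/mL at the last scheduled follow-up visit, with a substitute rule when that visit is missing.
- Definitions 2 and 3 use the decline from baseline plus stability within 0.2 log over the last three visits.
- Definition 4 is different in kind: "Three categories regarding the difference between HBsAg level at the last Follow-up timepoint and EOT". The categories are decreasing, stable and increasing, cut at 0.2 log10.

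One eligibility rule covers all four: "only participants with at least 24 weeks after JNJ-3989 stop will be used for the analysis". It sets no condition on when PegIFN or NA stopped.

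A footnote to SAP Table 2 says: "End of treatment (EOT) visit will be the last post-baseline visit in open-label phase as defined in" Table 1. For a participant who completes the open-label phase that is the Week 48 visit, Day 337. SAP 5.1.1 notes that the optional PegIFN "treatment phase, in contrast, may overlap with both the open-label and follow-up phases". SAP 1.2 has PegIFN "starting after the Week 40 biopsy (or after the optional leukapheresis if applicable) but before the Week 48 visit", and adds: "The duration (either 12 or 24 weeks) will be at the investigator's" discretion.

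The SAP version history gives the reason for adding 5.5.6: "Additional analysis for HBsAg was included to better characterize off-treatment HBsAg response". The same amendment added SAP 5.1.3, which ends the on-treatment period at the latest of last NA + 2 days, last PegIFN + 10 days and last JNJ-3989 + 28 days.

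**The concern.** For a PegIFN recipient, the value labelled EOT is usually taken during PegIFN treatment. Definition 4 then adds together two things that the section is meant to separate: the change while still on PegIFN, and the change after it stops. A participant who rebounds after PegIFN can be shown as stable or even decreasing, and one whose level merely holds after PegIFN can be shown as still decreasing.

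Protocol 2.1 says that PegIFN was offered to see whether it lowers HBsAg further, so a fall on PegIFN after Week 48 is the hoped-for effect and not a remote case.

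The eligibility rule raises a second, smaller question. Twenty-four weeks after JNJ-3989 stop can be a date on which PegIFN is still being given. It also puts in one denominator participants off NA, those who never stopped it and those who restarted it.

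**Working it through.** **The plan's own calendar.** Maximum participation is 126 weeks (protocol 4.1, SAP 1.2): 6 (screening) + 48 + 72 (extended follow-up) = 126. The figure reproduces. The 72 follow-up weeks are 24 + 48: PegIFN ending as late as FU Week 24, then 48 weeks of follow-up. The plan itself therefore expects PegIFN to run up to 24 weeks past EOT.

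**Inputs.**
- Week 48 / EOT is Day 337 and FU Week 24 is Day 337 + 168 = 505 (SAP Table 2). FU Week 48 is Day 337 + 336 = 673.
- JNJ-3989 is given "with the last injection at Week 44", Day 309.
- The Week 40 biopsy is nominally Day 281, ±4 weeks (protocol 1.3.1). PegIFN start s therefore runs from Day 282 (nominal biopsy) to Day 336.
- With weekly dosing, the last injection is s + 77 days (12-week course) or s + 161 days (24-week course). Under SAP 5.1.3 the PegIFN on-treatment period ends 10 days later.

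**Time on PegIFN after EOT** = (s + 7 × weeks − 337) / 7.

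| Course | Start | Weeks on PegIFN after Week 48 | On-treatment end |
|---|---|---|---|
| 12 wk | Day 282 | 4.1 | Day 369 |
| 12 wk | Day 336 | 11.9 | Day 423 |
| 24 wk | Day 282 | 16.1 | Day 453 |
| 24 wk | Day 336 | 23.9 | Day 507 |

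With the earliest permitted biopsy (Day 253, start Day 254) the lower ends drop to 0.1 and 12.1 weeks. For non-recipients, last JNJ-3989 + 28 days is 309 + 28 = Day 337, so EOT coincides with the SAP's own limit for that drug.

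**Definition 4.** Let f be the log10 fall on PegIFN after Week 48 and r the rebound after PegIFN. The change from EOT is r − f; the change from PegIFN end is r. From EOT, *increasing* requires r > f + 0.2; from PegIFN end it requires r > 0.2. Assumed values:

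| f | r | Against EOT | Against PegIFN end |
|---|---|---|---|
| 0.5 | 0.0 | Decreasing | Stable |
| 0.5 | 0.7 | Stable | Increasing |
| 1.0 | 0.7 | Decreasing | Increasing |
| 1.0 | 1.3 | Increasing | Increasing |

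**Eligibility.** The SAP does not say whether JNJ-3989 stop means the last injection or Week 48.
- From the last injection, 24 weeks is Day 309 + 168 = 477. A 24-week recipient is then between (477 − 453)/7 = 3.4 weeks off PegIFN and (507 − 477)/7 = 4.3 weeks short of its on-treatment end.
- From Week 48, it is Day 505: 7.4 weeks off to 0.3 weeks short.
- For a 24-week course started on Day 336, FU Weeks 16, 20 and 24 (Days 449, 477, 505) all precede Day 507. The three-visit check in Definitions 2 and 3 could then rest wholly on PegIFN values.
- At FU Week 48, recipients are (673 − 507)/7 = 23.7 to (673 − 369)/7 = 43.4 weeks off PegIFN after a nominal biopsy.

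**The case against.** Much of the case against a broad criticism stands.

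- Only Definition 4 uses EOT. A reader might infer that 5.5.6 as a whole masks rebounds after PegIFN. It does not: Definition 1 looks at the last scheduled visit and moves it later for recipients who stop NA during follow-up, and Definitions 2 and 3 check the last three visits and can detect a late rebound.
- A reader might infer that falls on PegIFN are counted as response. Definition 4 is a trend classification, and the SAP names none of its categories as response.
- A reader might infer a built-in advantage for PegIFN. Both groups use the same calendar point, and 5.5.6 specifies no comparison between them. What differs is where that point lies relative to the end of treatment.
- By FU Week 48, recipients are about 24 weeks or more off PegIFN, so a decline still present then is real.
- The off-treatment purpose appears in the version history and not in 5.5.6 itself. Outcomes with all treatment stopped are covered by functional cure (SAP 5.4.2.5) and the multiple-marker thresholds (SAP 5.4.2.4.9).
- SAP 5.1.6 and Table 6 allow splits by PegIFN use, and 5.5.6 plans individual plots coloured by category. No split is fixed for 5.5.6, however, and splitting leaves the reference value unchanged.

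None of this answers the point on Definition 4. Even at FU Week 48 its category still nets the fall on PegIFN against the rebound after it.

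**Conclusion.** The point holds for Definition 4 at every analysis. For most PegIFN recipients EOT is an on-PegIFN value, and a rebound of up to f + 0.2 log10 is not reported as an increase. This conflicts with the purpose given for the section and with the on-treatment rule added in the same amendment.

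The eligibility point is narrower. On-PegIFN or just-off-PegIFN values matter mainly at the FU Week 24 interim, which is optional but lists exploratory endpoints in SAP Table 7, and for participants whose last data fall near FU Week 24. The pooling of NA states applies throughout.

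A reader might infer from the 19.1% in the 200 mg arm of REEF-1 who met the NA completion criteria at Week 48 that most of the denominator here stays on NA. The documents do not support that for this trial. The figure comes from another study and takes no account of recipients who stop NA when PegIFN ends.

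The fall and rebound sizes above are assumptions; the documents give none for PegIFN in this trial. The calendar assumes visits on target days and complete weekly dosing. The endpoint is exploratory and descriptive, so this is a matter of correct labelling and interpretation and does not touch the primary result.

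**What to change.** In SAP 5.5.6:

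1. In Definition 4, take as reference the last HBsAg value on or before the later of last JNJ-3989 + 28 days and last PegIFN + 10 days. Apply the visit window (±3 days at Week 48), so that a slightly late Week 48 sample still serves for non-recipients. The Week 48 version can stay as a supplementary display.
2. For PegIFN recipients, count the 24 weeks of eligibility from that same date for all four definitions, again with the visit window. For the latest 24-week course the date is Day 507 + 168 = 675 against a nominal FU Week 48 of Day 673 (±4 days), so without the allowance some FU Week 48 values would be lost by chance.
3. Tabulate all four definitions by NA status at the last visit (off NA, never stopped, re-treated) and by PegIFN use. The NA term of SAP 5.1.3 is left out of the anchor on purpose, because this tabulation deals with NA.

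No new data are needed. Protocol 1.3.3 already schedules quantitative HBsAg at the end of PegIFN, on Day 85 or 169 of the course. That falls within last injection + 10 days (Day 78 + 10 = 88, or Day 162 + 10 = 172). The cost is SAP wording, some programming, and the loss of a few early leavers or interim-analysis participants from the denominator.

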5.6. Safety Analyses

All safety analyses will be based on the safety analysis set based on actual study intervention received, unless otherwise specified. Summaries will be provided on the overall population and by study panel and analysis phase unless specified otherwise.

For all continuous safety variables, descriptive statistics will include the N, mean, standard deviation, median, minimum, and maximum. Categorical variables will be summarized using frequency counts and percentages.

